11.8 Reporting of Pregnancy

Women entering the CF STORM will not be required to take a pregnancy test. Being pregnant is not an exclusion criteria per se, although it may be considered a non-CF condition that impacts on progress by the trial investigator and the patient.

If a woman becomes pregnant during the trial it should be recorded along with the outcome of the pregnancy (if applicable) on the CF STORM Module at each encounter and their annual review. However, if the pregnancy extends beyond the end of the follow-up period, then the pregnancy outcome will not be followed up.

11.9 Notification of Deaths

Any deaths which have been assessed and judged by the investigator to be "possibly", "probably" or "almost certainly" related to the dornase alfa (SARs) or hypertonic saline (Related SAEs) must be reported to the LCTC and the Chief Investigators within 24 hours of becoming aware using the "SAR Form" generated within the CF STORM Module. The death should also be reported within the Demographics section on tab '3. Diagnosis' within the UK CF Registry and manually transferred over to the CF STORM Module The patient should also be reported as withdrawn by completing the D8 tab in the CF STORM Module.

Any deaths which have not been assessed and judged by the investigator to be "possibly", "probably" or "almost certainly" related to the dornase alfa or hypertonic saline must be reported to the LCTC (within 7 days of becoming aware) via the Demographics section tab '3. Diagnosis within UK CF Registry and manually transferred over to the CF STORM Module. The patient should also be reported as withdrawn by completing the D8 tab in the CF STORM Module.

[figure not shown]
IRAS ID: 293186 Page **43** of **63**

12 REPORTING REQUIREMENTS

12.1 Reporting Procedures

All safety events which are recorded for the study should be reported following the procedures detailed below. The occurrence of a safety event may come to the attention of research staff during routine study visits, from the participant's notes, directly from the participant or by other means. Note that reporting procedures vary dependent on the nature of the incident (i.e. "serious" events are to be reported to LCTC in an expedited manner). Any questions concerning adverse event reporting should be directed to the LCTC in the first instance. A flowchart is given below to aid in determining reporting procedures for different types of adverse events.

12.1.1 Flowchart for Site Reporting Requirements of Adverse Events

12.1.2 Reporting Safety Events to the LCTC

All safety events (whether or not assessed as "serious" / "related" / "expected") should be recorded on the UK CF Registry under the "Complications tab". Intravenous antibiotics (dates and duration) and decline >10% in ppFEV $_1$ between consecutive encounters will be recorded on the UK CF Registry within 4 weeks of the event.

Safety events which are assessed as "serious" and "related" must **also** be recorded in more detail on the "SAR form" which can be found within the CF STORM Module; a single form is used for each individual event

IRAS ID: 293186 Page **44** of **63**

(i.e. a single diagnosis), though multiple symptoms can be recorded. *N.B. this includes events assessed as either "related" to the dornase alfa IMP (i.e. SARs) and events assessed as "related" to the hypertonic saline trial procedure (i.e. Related SAE).*

Where additional information is received by site after initial submission to LCTC, this should be updated on the "SAR form" within 5 days. The "SAR form" collects data regarding the nature of event, date of onset, severity, corrective therapies given, outcome and causality; all serious events reported to LCTC will be reviewed by a Co-Chief Investigator and assessed for causality and expectedness.

12.1.3 Follow-up After Adverse Events

All reportable adverse events should be followed until satisfactory resolution or until the investigator responsible for the care of the participant deems the event to be chronic or the patient to be stable.

When reporting "serious" safety reactions the investigator responsible for the care of the participant should apply the following criteria to provide information relating to event outcomes:

- resolved
- resolved with sequelae (specifying with additional narrative)
- not resolved/ongoing
- ongoing at final follow-up
- fatal or unknown.

12.2 Investigator Reporting Responsibilities

The PI is responsible for ensuring that all safety events requiring recording on this study (see section 12.1) which the local research team becomes aware of are reported to LCTC. It is the responsibility of the PI/Co-I as recorded on the Delegation Log (medically qualified person) to assess the seriousness and causality of events. When documenting any adverse events, the correct medical terminology must be used in accordance with MedDRA.

All safety events must be recorded on the "Complications tab" within seven days of the site team becoming aware of the event.

Safety events which meet the definition of "serious" and "related" must be reported in more detail to the LCTC on the "SAR form" and reported **immediately and in no circumstances later than 24 hours from becoming aware** where they will be appropriately processed.

The "SAR form" should be completed by an appropriately delegated member of the research team; the assessments of seriousness and causality must be performed by an appropriately medically qualified person. Minimum reporting information* must be provided in initial reports for all studies.

The minimum information* required for reporting is as follows:

- Valid EudraCT number
- Sponsor trial number
- One identifiable coded subject
- One identifiable reporter
- One safety event
- One suspect product (including active substance name)
- A causality assessment.

Safety events should also be reported to the site R&D team in accordance with local policy.

REPORTING AN INITIAL OR FOLLOW-UP SAR / Related SAE

The investigator should ensure the actions below are completed for all reportable SARs / Related SAEs:

IRAS ID: 293186 Page **45** of **63**

- 1) The complication (AE) should be marked as 'serious' on the CF STORM Module.
- 2) The LCTC will receive an alert email to alert them that the SAR criteria has been met (only for AEs assessed as "serious" and "related").
- 3) The responsible investigator will then complete the "SAR form" within the CF STORM Module and provide sign off (immediately, within 24 hours).
- 4) The LCTC will receive an alert email to notify them that a "SAR form" has been completed.
- 5) The responsible investigator must notify their R&D department of the event (as per standard local governance procedures).
- 6) The patient must be identified by trial number **only**. The patient's name **should not** be used on any correspondence.
- 7) SARs / Related SAEs must be subsequently followed up in line with the processes below:
 - Follow up must continue until clinical recovery is complete and laboratory results have returned to normal, or until the event has stabilised (see Section 11.7.4). N.B. Follow-up may continue after completion of protocol treatment if necessary.
 - Follow-up information should be entered onto the CF STORM Module and submitted as soon as more information becomes available if the event has not resolved at the time of initial report.

In the event of a problem with the CF STORM Module (power failure, server failure etc.) please contact the LCTC.

Participant safety incidents that take place in the course of research should be reported to the National Reporting and Learning System (NRLS) by each participating NHS Trust in accordance with local reporting procedures.

12.3 **LCTC Responsibilities**

The trial Sponsor, Alder Hey Children's NHS Foundation Trust have delegated to LCTC the duty of onward reporting of safety events to REC and MHRA. SOPs will be followed to ensure appropriate reporting as detailed below.

The LCTC Central Safety Team will alert the Chief Investigators (or Medical Reviewers) within 24 hours of receiving the minimum information of a SAR / Related SAE from site. One of the Co-Cls will review information provided by site and will provide an assessment of "expectedness".

Safety events which are assessed as "serious", "related" to the trial IMP dornase alfa and "unexpected" (i.e. SUSARs) will be expedited to the REC and the MHRA within the following timeframes:

- SUSARs which are fatal or life-threatening as soon as possible and in any case no later than **7 days** after the LCTC receives the legal minimum information. If the initial report is incomplete, a complete report will be submitted within an additional 8 days.
- SUSARs that are not fatal or life-threatening **within 15 days** of the LCTC receiving the legal minimum information.

Additionally, SUSARs will be reported to the trial Sponsor and Principal Investigators of participating sites within the agreed timelines. The LCTC will submit an Annual Safety Report to REC and a Development Safety Update Report to the MHRA on an annual basis.

Safety events which are assessed as "serious", "related" to the trial device procedure hypertonic saline and "unexpected" (i.e. RUSAEs) will be reported to the originating site within 7 days in order for them to perform applicable local reporting requirements. RUSAEs will not be expedited to MHRA or REC by LCTC.

New events related to the conduct of the trial and likely to affect the safety of the participants, such as the below statement should be reported in an expedited fashion:

 Recommendations of the Independent Data and Safety Monitoring Committee, if any, where relevant for the safety of the participants.

IRAS ID: 293186 Page **46** of **63**

The PIs at all institutions participating in the trial will be notified of any SUSARs/RUSAEs within a reasonable timeline. Any concerns raised by the TSC/IDSMC or inconsistencies regarding safety reporting noted at a given site may prompt additional training at sites, with the potential for the LCTC to carry out site visits if there is suspicion of unreported safety events in patient case notes. Additional training will also be provided if there are unacceptable delays in safety reporting timelines.

12.3.1 Safety Reports

Safety reports will be generated during the course of the trial which allows for monitoring of safety event including reporting rates and safety events by site / arm. The LCTC will send annual reports containing a list of all SARs to the MHRA and REC, the IDSMC will receive both SARs and Related SAEs. If any safety reports identify issues that have implications for the safety of trial participants, the PIs at all institutions participating in the trial will be notified.

12.3.2 Urgent Safety Measures (USMs)

An urgent safety measure (USM) is a procedure to protect clinical trial participants from any immediate hazard to their health and safety but has not previously been defined by the protocol. It can be put in place prior to authorisation by the REC and the MHRA.

The Sponsor or delegate will notify the MHRA and REC immediately and, in any event, within 3 days that such a measure has been taken and the reasons why it has been taken. The initial notification to the REC and MHRA will be by telephone (ideally within 24 hours) and a notice in writing will be sent within 3 days, setting out the reasons for the USM and the plan for further action. After discussion with the REC and MHRA, further action will be agreed, which may include submission of a substantial amendment, a temporary halt, or permanent termination of the trial.

Following notification, if a substantial amendment is required this must be submitted as soon as possible to the REC and ideally within two weeks to the MHRA. If the study is temporarily halted it may not recommence until authorised to do so by the REC and MHRA. If the study is permanently terminated before the date specified for its conclusion (in the original applications to REC and MHRA), the Sponsor should notify the REC and MHRA within 15 days of the date of termination by submitting the formal End of Trial Notification.

12.4 Contact Details and Out-of-hours Medical Cover

As IMP is used as standard NHS practice emergency and out-of-hours medical care will be in line with usual NHS arrangements and local standard practice; no special provision is required for CF STORM participants. All participants will be provided with a copy of the information sheet which includes information about their participation and contact details for the local research team who may be contacted if necessary. During office hours, the CI or delegate are able to provide medical advice in relation to participation using the contact details listed at the beginning of this document.

IRAS ID: 293186 Page **47** of **63**

13 STATISTICAL CONSIDERATIONS

13.1 Sample Size

13.1.1 Sample Size Calculation

For the power calculation, we have used published UK CF Registry data that map the change in ppFEV₁ in a smaller population of pwCF established on a similar highly effective mutation specific therapy (ivacaftor), a significant proportion of whom were on dornase alfa.(11)

We have used the larger Standard Deviations for ppFEV₁ from the results of the post-market surveillance UK CF Registry trial, as these data better represent our patient population, longer duration of follow-up and registry-based data collection. (11)

The non-inferiority margin was determined using the approach recommended by Food and Drug Administration (FDA) guidelines (https://www.fda.gov/media/78504/download), referred to as the fixed margin method, which involves a combination of statistical and clinical considerations. The percentage is conventionally set at 50%, i.e. the non-inferiority margin is half the lower Confidence Interval (CIn) limit of the established (ivacaftor-comparator) rate. (12) The difference in mean change (95% CIn) of ppFEV₁, based on data (presented at 2016 North American CF Conference) from Volkova et al. was 8.1 (6.51, 9.69), and therefore half of the lower limit of the 95% CIn is just over three.(11) This is consistent with the limit difference determined for the CF SIMPLIFY trial.

Finally, we triangulated these calculations with PPI and stakeholder input to confirm the acceptability of the limit difference of 3%.

A sample size of 343 in each arm (with a one-sided 0.025 significance level) will have a 90% power to reject the null hypothesis that removing nebulised mucoactive therapy ("STOP") is worse than continuing nebulised mucoactive therapy ("CONTINUE") by a mean difference of more than 3 or farther from zero in the same direction in favour of the alternative hypothesis that removing nebulised mucoactive therapy ("STOP") is not worse than continuing nebulised mucoactive therapy ("CONTINUE") by a mean difference of more than 3 or farther from zero in the same direction i.e. the means are non-inferior, assuming that the expected difference in means is 0 and the common standard deviation is 12.1.

Based on information from previous trials in the field of CF, we do not anticipate that missing data will be above 10%. We have inflated the sample size by 10% and a total of 382 participants will be randomised to each treatment group (764 participants in total).

13.1.2 Sample Size Revision

Following significant challenges to recruitment, it was agreed with the trial funder to reduce the statistical power from 90% to 80% to ensure that the trial is delivered in a reasonable time frame. The reduced power was considered acceptable by the TMG and independent oversight committees, and in conjunction with new trial data (13) would provide strong evidence to inform clinical practice.

To reach 80% power, a sample size of 257 in each group is required. Allowing for 10% dropout requires 286 patients in each group, giving a total of 572 participants. 90% power requires 343 patients to be recruited in each group, giving a total of 686 participants overall. Allowing for 10% dropout requires 382 in each group, giving a total of 764 overall. We aim to recruit a minimum of 80% power.

13.1.3 Feasibility of Sample Size

Sites will open remotely with support and training from the CF STORM team. The trial has been badged by CTAP and the CTAP trial co-ordinators support site opening, recruitment and trial management in each of

IRAS ID: 293186 Page **48** of **63**

their centres. In addition, we will include centres outside the CTAP network, who meet site suitability criteria (see section 6).

13.2 Method of Randomisation

13.2.1 Allocation Sequence Generation

The allocation sequence will be generated by a statistician who is independent to the trial team. Randomisation lists will be generated in a 1:1 ratio using simple block randomisation with random variable block length. Factors within this protocol that are being used to stratify randomisation will not be disclosed to prevent prediction in this open trial.

13.2.2 Concealment and Implementation of Allocation Sequence

Patient allocations will be irrevocably generated upon completion of the web-based randomisation form by a delegated member of the trial research team. Allocation concealment will be ensured as the service will not release the randomisation code until the patient has been recruited into the trial; this takes place after all baseline measurements have been completed.

13.3 **Interim Analyses**

No formal interim analyses of primary or secondary outcomes will be performed but analyses of the accumulating data (recruitment, protocol deviations, baseline characteristics, compliance, withdrawals, missing data and safety data) will be performed at regular intervals (at least annually) for review by an IDSMC.

These analyses will be performed by the LCTC trial statistician. The IDSMC will be asked to give advice on whether the accumulated data from the trial, together with results from other relevant trials, justifies continuing recruitment of further participants or further follow-up. A decision to discontinue recruitment, in all participants or in selected subgroups will be made only if the result is likely to convince a broad range of clinicians including participants in the trial and the general clinical community. If a decision is made to continue, the IDSMC will advise on the frequency of future reviews of the data on the basis of accrual and event rates. All closed results (results split by treatment) will be confidential to the IDSMC members and will not be for review by the trial management group (except the statistical team preparing the IDSMC report). The IDSMC members will make formal recommendations to the TMG and TSC (see section 4.3) regarding the continuation of recruitment of participants into the trial and will comply with a trial-specific IDSMC charter.

The IDSMC will be asked to consider participant safety, particularly any Suspected Unexpected Serious Adverse Reactions (SUSARs) leading to death, alongside treatment efficacy when making their recommendation regarding continuation, amendment or discontinuation of the trial.

13.4 **Analysis Plan**

A full statistical analysis plan (SAP) will be written prior to the conduct of any comparative analysis of the treatment arms. The main features of the SAP are summarised below:

Analyses will be conducted using the intention to treat principle with a 2.5% level of statistical significance and one sided 97.5% Clns. The primary outcome, and other continuous outcomes (including quality of life scores) will be analysed using analysis of covariance adjusted for baseline score. The primary analysis will also be adjusted for the stratification factors used in randomisation.

Non-inferiority of the "stop nebulised therapy" group will be accepted in a 0.025 level test, if the lower bound of the one sided 97.5% Clns in means in the primary outcome lies above -3.

IRAS ID: 293186 Page **49** of **63**

Given that poor study conduct quality (including eligibility violations, poor adherence, treatment crossovers and missing data) typically leads to a dilution of the treatment effect, and thus an increased probability of falsely concluding non-inferiority, we will supplement intention to treat analyses with appropriate causal methods to adjust for treatment crossovers rather than rely on per protocol or as treated analyses (which are typically subject to selection biases).

Missing data will be handled by considering the robustness of the complete case analysis to sensitivity using various imputation assumptions. These assumptions will be informed by data collected on the reasons for missing data.

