6 STUDY DESIGN

CF STORM is designed as a randomised, open-label, non-inferiority trial with 1:1 allocation ratio.

Through extensive PPI consultation we constructed a trial design that is pragmatic and reflects the lived experience of pwCF. The trial will randomly allocate patients 1:1 to either 'STOP' or 'CONTINUE' their existing daily nebulised mucoactive therapies (stratified by clinical site and nebulised mucoactive treatment(s) at enrolment; with data from the UK CF Registry we have modelled stratification of randomisation for different number and sizes of sites). Non-inferiority margins, will provide confidence that stopping mucoactive therapies is not associated with a significant decrease in ppFEV₁ over the 12-month trial period.

6.1 **Blinding**

This is an open label study with no blinding requirements.

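### The stated analysis adds the randomisation strata to the primary model only, so continuous secondary outcomes get conservative intervals if site and nebulised treatment stay prognostic after baseline adjustment

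*Protocol*

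**What the plan says.** Section 6 of the protocol has 1:1 allocation "stratified by clinical site and nebulised mucoactive treatment(s) at enrolment". Section 13.2.1 describes the lists: "Randomisation lists will be generated in a 1:1 ratio using simple block randomisation with random variable block length".

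Section 13.4 opens its account of the analysis with "The main features of the SAP are summarised below". It then groups the primary outcome with the rest of the continuous outcomes under one model: "other continuous outcomes (including quality of life scores) will be analysed using analysis of covariance adjusted for baseline score". The next sentence adds the strata, and names only one analysis: "The primary analysis will also be adjusted for the stratification factors used in randomisation". The section gives no model for counts or events. The testing framework is a "2.5% level of statistical significance and one sided 97.5% Clns". A non-inferiority decision rule is given for the primary outcome alone: "if the lower bound of the one sided 97.5% Clns in means in the primary outcome lies above -3".

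The continuous secondary outcomes with a baseline and a 52-week value are listed in section 9.2: ppFVC, ppFEF25-75, weight, height and BMI, and the CFQ-R total and domain scores.

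**The concern.** Blocking within strata makes the two arms alike on site and on nebulised treatment. If these factors predict the outcome, the treatment difference varies less from trial to trial than it would under unrestricted allocation. A model without the strata does not see this. It leaves the between-stratum variation in the residual and reports a standard error that is too large. The intervals are then wider than the design warrants, and the tests run below their nominal level.

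The text goes beyond silence on a detail. It puts the primary and the other continuous outcomes under one model and then adds the strata for the primary analysis. An SAP that followed these main features would leave the strata out of the others.

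The protocol gives some reason to think that the factors are prognostic. Section 8.6 links use of dornase alfa alone with less severe lung disease. Table 1 shows a treatment mix that differs by centre type (both drugs: 25% in adult and 41% in paediatric centres). How much of this remains once the baseline value is in the model is not known. What is at stake is some precision on outcomes such as quality of life and nutrition, which section 5.4.2 lists as secondary objectives.

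**Working it through.** **1. The plan's own figure.** Section 13.1 gives a margin of 3, one-sided 0.025, and the sample size is calculated "assuming that the expected difference in means is 0 and the common standard deviation is 12.1". The normal approximation is n per arm = 2(z_0.975 + z_power)² × 12.1² / 3².

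- 80% power: 2 × (1.960 + 0.842)² × 146.41 / 9 gives 256. With the noncentral t it is 257, as stated. 257/0.9 gives 286 per group.
- 90% power: the same steps give 342. With the noncentral t it is 343, as stated. 343/0.9 gives 382 per group.

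The sample size reproduces. It takes no credit for the strata and concerns the primary outcome only, so this point does not touch it.

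**2. Effect of leaving out the strata.** Let R² be the share of the baseline-adjusted variance that site and nebulised treatment explain. The protocol gives no value, so R² is an assumption shown as a range. In a linear model under stratified randomisation:

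- unadjusted width / adjusted width = 1/√(1 − R²)
- true level of a nominal one-sided 0.025 test = 1 − Φ(1.96/√(1 − R²))

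For R² = 0.10: 1/√0.90 = 1.054, and 1 − Φ(1.96 × 1.054) = 0.0194.

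**3. Cost of the site terms.** A simulation used 514 analysed patients (2 × 257), block-stratified allocation, three treatment strata in the Table 1 proportions (2471 : 330 : 1766), and site as fixed effects. The number of sites, 16 or 40, is assumed.

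| Assumed residual R² | Width ratio, formula | True level of nominal 0.025 | Simulated ratio, 16 sites | Simulated ratio, 40 sites |
|---|---|---|---|---|
| 0 | 1.000 | 0.0250 | 0.998 | 0.991 |
| 0.01 | 1.005 | 0.0244 | – | – |
| 0.05 | 1.026 | 0.0222 | 1.017 | 1.009 |
| 0.10 | 1.054 | 0.0194 | 1.038 | 1.032 |
| 0.20 | 1.118 | 0.0142 | 1.086 | 1.078 |

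The first row isolates the price of fixed site terms when the strata explain nothing: about 0.2% of width with 16 sites and 0.9% with 40. In that case adjustment makes the interval slightly wider.

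**4. Why the simulated ratios fall below the formula.** Most of the gap is not the cost of the site terms. The simulation draws the site and treatment effects at random, and in the sample they explain less than the nominal R². With 16 sites the unadjusted width falls from 4.192 at R² = 0 to 4.089 at a nominal 0.20. The total variance is therefore (4.089/4.192)² = 0.951 of its nominal value, and the realised share is 1 − 0.80/0.951 = 0.159. Then 1/√(1 − 0.159) × 0.998 = 1.088, close to the simulated 1.086.

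Taking only the site-term cost off the formula gives, for 16 and 40 sites, 1.024 and 1.017 at R² = 0.05, 1.052 and 1.045 at 0.10, and 1.116 and 1.108 at 0.20.

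**The case against.** The strongest reply is that covariate lists for secondary outcomes belong in the SAP, that section 13.4 is only a summary, and that it nowhere says the secondary outcomes will be left unadjusted. This stands in part: the SAP is not at hand and may extend the adjustment. But the protocol draws a contrast between analyses it has just put under one model, and that contrast is worth correcting where it is written.

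Other parts of the reply stand in full, because a reader might infer more than the text supports:

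- *That every secondary outcome is adjusted for baseline alone.* The protocol says this of continuous outcomes only. It gives no model for exacerbations, antibiotic courses or admissions, and the width formula for linear models does not carry over directly to count or event models. In a logistic model, for instance, adjustment also changes which odds ratio is estimated.
- *That the intervals are certainly wider.* This depends on how prognostic the strata are after baseline adjustment. At R² near 0 there is nothing to gain.
- *That this makes stopping look safer.* A wider interval moves the harm-side bound further towards harm, so harm is harder to rule out. The inference needs a reader who takes a non-significant secondary result as proof of safety. The protocol sets no such rule and no margin for any secondary outcome.
- *That adjustment has no downside.* The footnote to Table 1 says that many paediatric sites are small clinics. Site terms there can be poorly estimated.

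**Conclusion.** The point holds for the continuous secondary outcomes and is modest in size. As written, these models omit the factors used to randomise. If the factors remain prognostic, the standard errors are overstated: by formula 2.6%, 5.4% or 11.8% in interval width at an assumed residual R² of 5%, 10% or 20%, and about 0.2 to 0.9 percentage points less once fixed site terms are paid for at 16 or 40 sites. The R² values and the numbers of sites are assumptions. At R² near 0 the gain vanishes or reverses slightly.

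The error is on the conservative side. Type I error is not inflated, and neither the primary non-inferiority conclusion nor the sample size changes. The protocol does not support a claim that safety conclusions are biased in favour of stopping, or any claim about how counts and events will be modelled.

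**What to change.** Amend the sentence in section 13.4 so that the models for the primary and for the continuous secondary outcomes all adjust for baseline score and for the stratification factors: nebulised treatment at enrolment as a fixed effect, and site as a random effect or with small sites pooled. Add that the same factors enter the count and event models where they can be estimated. State the fallback in advance: if a model fails to converge or sites are too sparse, pool sites or drop the site term, in a fixed order.

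The cost is a sentence or two and the same wording in the SAP. No new data are needed, since site and treatment at enrolment are known for every randomised participant. The downside is small and confined to sparse sites and possible non-convergence, which the fallback covers. The change should be made before any comparative analysis, so that the covariates are not chosen after results by arm have been seen.
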